4.2.3 Sensitivity analyses

4.3 Secondary endpoints analysis

4.3.1 Key secondary endpoints

4.3.1.1 Definition of endpoints

4.3.1.1.1 PASI75 response at Week 4

The binary response endpoint PASI75 at Week 4 is defined to be equal to 1 if the percentage improvement from Baseline to Week 4 in the PASI scores is 75% or greater and 0 if the percentage improvement from Baseline to Week 4 is less than 75%. This definition is introduced for the purpose of identifying study participants who respond to the treatment (1 = responder, 0 = non-responder).

Detailed information for PASI and the definition of percentage improvement from Baseline can be found in Section 6.8.2.

4.3.1.1.2 PASI100 response at Week 16

PASI100 response at Week 16 is defined to be equal to 1 if the percentage improvement from Baseline to Week 16 in the PASI scores is 100% and 0 if the percentage improvement from Baseline to Week 16 is less than 100%. This definition is introduced for the purpose of identifying study participants who respond to the treatment (1 = responder, 0 = non-responder).

Detailed information for PASI and the definition of percentage improvement from Baseline can be found in Section 6.8.2.

4.3.1.2 Main analytical approach

The key secondary efficacy endpoints will be analyzed for all study participants in the RS. The primary analysis will be based on the CMH test as specified in Section 4.2.2. If one of the treatment groups has 0 or very low response where CMH is no longer an appropriate method, Fisher's exact method will be applied instead, odds ratio and associated 95% CI will not be provided.

NRI will be used to account for missing data in the primary analysis. Specifically, any study participant who permanently withdraws from IMP prior to the given time point of interest or who has missing data for the key secondary efficacy variables at the given time point of interest will be considered as a non-responder.

The number and percentage of study participants who are PASI75 responders at Week 4 and PASI100 responders at Week 16 will be summarized separately for the RS.

Line plots of the PASI100 responder rate over time by treatment group will be produced.

By-study participant listings of PASI75 and PASI100 responder variables will be provided for the RS.

4.3.1.3 Sensitivity analyses

Sensitivity analysis based on OC will be performed for the RS. Study participants with missing data or who have prematurely discontinued IMP will be treated as missing, and missing data will not be imputed. The same analysis method as described in Section 4.3.1.2 will be applied.

[figure not shown]
4.3.2 Additional secondary endpoints

The PSD (P-SIM) consists of 14 items, measuring the following PSO related signs, symptoms, and functional impacts: [REDACTED]

[REDACTED]. Each item is assessed for severity/impact level on a 0 to 10 scale, where 0 means no symptoms or impact and 10 means very severe symptoms or worst impact.

The additional secondary efficacy endpoints will be derived as follows:

- PSD (P-SIM) response for itch at Week 16: Itch score has improved (decreased) by ≥ 4 points from Baseline to Week 16, and the study participant has not discontinued IMP prior to Week 16. This will be assessed only in study participants with a Baseline itch score ≥ 4 .
- PSD (P-SIM) response for pain at Week 16: Pain score has improved (decreased) by ≥ 4 points from Baseline to Week 16, and the study participant has not discontinued IMP prior to Week 16. This will be assessed only in study participants with a Baseline pain score ≥ 4 .
- PSD (P-SIM) response for scaling at Week 16: Scaling score has improved (decreased) by ≥ 4 points from Baseline to Week 16, and the study participant has not discontinued IMP prior to Week 16. This will be assessed only in study participants with a Baseline scaling score ≥ 4 .

4.4 Tertiary/Exploratory endpoints analysis

The tertiary efficacy endpoints in the Initial Treatment Period + Maintenance Treatment Period (combined) will be analyzed for all study participants in the RS.

4.4.1 Binary endpoints

The binary tertiary efficacy endpoints are listed as follows:

- IGA 0 response over time
IGA 0 response is defined as IGA score of zero with at least a two-category improvement from Baseline at visit timepoint.
- IGA 0/1 response over time
- PASI75 response over time
- PASI90 response over time
- PASI100 response over time
- Percentage of study participants with absolute PASI score ≤ 1 , ≤ 2 , ≤ 3 , and ≤ 5 over time
- Scalp IGA 0/1 response over time

Details about scalp IGA can be found in section 6.8.4. Scalp IGA 0/1 response is defined as scalp IGA score of clear [0] or almost clear [1] with at least a two-category improvement from Baseline to each post baseline time point. For analysis purposes, the evaluation of scalp IGA will be limited to study participants with a Baseline scalp IGA of at least 2. Therefore, if a study participant has a score of 2 at Baseline, they can only be considered a responder if their scalp IGA is 0 (thereby meeting the criterion for a two-category improvement from Baseline). Study participants with a Baseline scalp IGA of 1 will be assessed per the protocol but will not be part of the scalp IGA 0/1 response analysis.

- DLQI 0/1 response over time
Details about DLQI can be found in section 6.8.5. DLQI 0/1 response is defined as DLQI absolute score of 0 or 1.

In addition to the aforementioned tertiary endpoints, the following summaries will be provided:

- Percentage of study participants with absolute BSA = 0%, $\leq 1\%$, $\leq 3\%$ and $\leq 5\%$ over time
- DLQI minimally clinical important difference (MCID) response over time

A study participant is considered to have achieved MCID if their individual improvement (decrease) from Baseline score is ≥ 4 (Basra et al, 2015). A 4-point improvement in the DLQI score (DLQI response) has been reported to be meaningful for the study participant (within-study participant MCID). The summary of MCID will be restricted to study participants with a DLQI of at least 4 at Baseline to ensure that it is possible for the study participant to achieve the MCID.

Binary (response) endpoints will be summarized using frequency tables by treatment group for each visit.

All binary tertiary efficacy endpoints will be summarized based on imputed data (NRI) and OC data (ie, study participants with missing data or who have prematurely discontinued IMP are treated as missing, study participants with missing data will not be included in OC analysis), unless otherwise stated.

Summaries of MTP data among Week 16 responders only for PASI90, PASI100, IGA 0/1, IGA 0, Scalp IGA 0/1, DLQI 0/1 will be provided based on MS respectively.

Figures displaying the response over time using NRI data will be provided for PASI 90/100, IGA 0, IGA 0/1, Scalp IGA 0/1 and DLQI 0/1 response variables.

4.4.2 Continuous endpoints

The continuous tertiary efficacy endpoint is change from Baseline over time for each PSD (P-SIM) item score.

Continuous variables will be summarized using descriptive statistics by treatment group for each visit based on OC. Summaries of observed values and change from Baseline over time for DLQI score will also be provided.

In addition, cumulative distribution plots (see details in Section 4.3.2) will be provided for absolute and percent change from Baseline PSD at Week 16 for each item.

4.4.3 Time to PASI75/90/100 response

Time to PASI75/90/100 response (in days) during the ITP will each be calculated as:

Min (Date of first PASIxx response, Date of Week 16 visit) – Date of First Dose + 1

with xx representing 75, 90, 100 respectively. All visits up to and including Week 16 visit (including unscheduled visits) will be considered.

Study participants who discontinue IMP without achieving a given PASI response (either PASI75, PASI90, or PASI100 response, respectively) prior to Week 16 visit will be censored at the date of the last observed PASI assessment on or prior to IMP discontinuation. Study participants who reach the Week 16 visit without achieving the given PASI response will be censored at the date of the last observed PASI assessment on or prior to the Week 16 visit. Study participants who miss the Week 16 visit but start the MTP without achieving a give PASI response will be censored at the date of the last observed PASI assessment on or prior to the first IMP administration in MTP. Study participants will be censored at Baseline if there is no Baseline PASI assessment or no post-Baseline PASI assessment.

Time to PASI75/90/100 response during the ITP will each be estimated and presented using the Kaplan-Meier product-limit method for each treatment group.

Kaplan-Meier plots of time to PASI responses will also be presented by treatment group. In these Kaplan-Meier plots, the line will start at 0 (since there are no responders at Day 0) and will increase over time, representing time to achieving the response.

The median time to response, including the 2-sided 95% CI, will be calculated for each treatment group. Comparisons of bimekizumab versus placebo will be analyzed using a log-rank test.

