9.3.3 Tertiary efficacy endpoint analyses

The tertiary efficacy endpoints in the Initial Treatment Period and the Overall Treatment Period (Initial Treatment Period+Maintenance Treatment Period) will be analyzed for all study participants in the RS.

Binary (responder) endpoints will be summarized using frequency tables by treatment group for each visit. Continuous endpoints will be summarized using descriptive statistics by treatment group for each visit.

Time to PASI75/90/100 response during the Initial Treatment Period will be estimated and presented using the Kaplan-Meier product-limit method for each treatment group. Time to a given response will be defined as the length in days from the first dose of IMP until the first date when the response is achieved. Study participants who discontinue IMP prior to achieving a response will be censored at the date of IMP discontinuation. Study participants who reach the Week 16 visit without achieving the given PASI response will be censored at the date of the Week 16 visit. Study participants will be censored at Baseline (Day 0) if there is no Baseline PASI assessment or no post-Baseline PASI assessment. The median time to response, including the 2-sided 95% CI, will be calculated for each treatment group. Comparisons of bimekizumab versus placebo will be analyzed using a log-rank test.

All binary tertiary efficacy endpoints will be summarized based on imputed data (NRI), unless otherwise stated in the SAP. In some cases, endpoints may also be summarized based on observed case data (ie, study participants with missing data or who have prematurely discontinued IMP are treated as missing). Should there be no missing data for a study endpoint, then only observed case data will be presented. Continuous variables will be summarized using descriptive statistics by treatment group for each visit based on observed case.

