Derived variables in general will display the mean, SD and median to 1 more decimal place than the variables used in the derivation. If the number of decimal places reported in the raw data is varied then use either the maximum raw number of reported decimal places or 3, whichever is the lowest, as a guide for the descriptive statistics.

Statistical tests of efficacy variables will be presented as two-sided p-values rounded to three decimal places. P-values less than 0.001 will be presented as “<0.001” and p-values greater than 0.999 will be presented as “>0.999”. Statistical comparisons will be two-sided and will be performed at the 0.05 level of significance.

A complete set of data listings containing all documented data as well as calculated data (eg, change from Baseline) will be generated.

Unless otherwise stated, the IMP administration in the Maintenance Treatment Period includes both active IMP (bimekizumab) and placebo injections for study participants randomized to BKZ Q4W in the initial treatment period and switch to BKZ Q8W in the Maintenance Treatment Period.

Per protocol, for visits from the first dose of IMP through Week 32, the visit window is ± 4 days from the scheduled visit. For the SFU Visit, the visit window is ± 7 days from the scheduled visit. All by-visit summaries will contain nominal (ie, scheduled) visits only. Unscheduled visits will not be mapped to scheduled visits except for assessments that occur within a 4-day time window of a scheduled visit and the relevant scheduled visit data is not available. In that case, the assessment will be mapped to the corresponding scheduled visit and will be used for the analysis. If multiple unscheduled visits are remapped to one scheduled visit, the data collected on a day nearest to the scheduled visit day will be used in the analysis. This will only occur for some vendor data (questionnaire data such as PASI, IGA, PSD, scalp IGA, and DLQI data).

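### Censoring Week 16 nonresponders on their own visit date makes the Kaplan-Meier curves for time to PASI75/90/100 overstate cumulative response at the Week 16 end

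*SAP*

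**What the plan says.** SAP 4.4.3 defines the time variable from calendar dates: "Min (Date of first PASIxx response, Date of Week 16 visit) – Date of First Dose + 1". Unscheduled visits up to Week 16 count. The censoring rule begins: "Study participants who reach the Week 16 visit without achieving the given PASI response will be censored at the date of". The date meant is that of the last PASI: such a participant "will be censored at the date of the last observed PASI assessment on or prior to the Week 16 visit". Protocol 9.3.3 has such a participant leave "without achieving the given PASI response will be censored at the date of the Week 16 visit". The two rules coincide for anyone with a PASI at Week 16.

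SAP 4.1 says that "for visits from the first dose of IMP through Week 32, the visit window is ± 4 days from the scheduled visit". The schedule of activities has PASI at Baseline and Weeks 1, 2, 4, 8, 12 and 16, with no scheduled reading between Weeks 12 and 16.

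From these times SAP 4.4.3 plans Kaplan-Meier estimates and plots per arm, a median with a 95% confidence interval per arm, and a log-rank test. SAP 4.1 also has a nominal-visit rule: "All by-visit summaries will contain nominal (ie, scheduled) visits only". That rule does not reach this analysis. Neither document sets nominal time, a common censoring day or an interval-censored method here.

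**The concern.** PASI response is only seen at visits. A nonresponder read on Day 109 and a responder read on Day 117 have both completed the Week 12 to 16 interval. Kaplan-Meier on actual dates does not treat them that way. It drops the first person on Day 109, assumes that this person could still respond on Days 110 to 117, and divides the later responders by a shrinking risk set. The risk that belongs to one assessment is applied again on each day of the window.

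Earlier visits do not have this problem to any extent, because their nonresponders stay at risk. At Week 16 every remaining nonresponder is censored inside the window.

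At stake are the right-hand end of three published curves in each arm and, under a condition given below, the median. A curve can also run to 100% if the last person seen in an arm is a first-time responder.

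**Working it through.** The plan prints no figure for this endpoint, so there is nothing to reproduce. The check derives what the stated rules produce.

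**Inputs from the documents.** 90 participants on bimekizumab and 30 on placebo. Week 16 is Day 16 × 7 + 1 = 113, so the window is Days 109 to 117, which is 9 days.

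**Assumptions, not in the documents.** Cumulative first response F12 by Week 12 and F16 by Week 16, no dropout, and visit day independent of response. Visit days are spread evenly, spread in a triangle around Day 113, or placed 50% or 80% on Day 113 with the rest in the window.

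**Formula.** Among those still without response after Week 12, the share responding at Week 16 is p = (F16 − F12)/(1 − F12). If w_d is the share of visits on day d and R_d the share on day d or later, the large-sample end of the curve is

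KM = 1 − (1 − F12) × ∏(1 − p·w_d/R_d).

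With evenly spread visits, w_d/R_d runs 1/9, 1/8, …, 1/1, so the product is ∏(1 − p/k) for k = 9 down to 1.

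**Worked case, 45%/60%, even spread.** p = 0.15/0.55 = 0.273. The nine daily factors are 0.970, 0.966, 0.961, 0.955, 0.945, 0.932, 0.909, 0.864 and 0.727. Their product is 0.432. The correct factor is applied once: 1 − 0.273 = 0.727.

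- Plan as written: 1 − 0.55 × 0.432 = 0.76.
- Correct: 1 − 0.55 × 0.727 = 0.60.

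**Finite samples.** Simulated final Kaplan-Meier estimate, range over the visit-day patterns:

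| Arm size | Assumed F12/F16 | Kaplan-Meier at the end |
|---|---|---|
| 90 | 45%/60% | about 76-80% |
| 90 | 30%/40% | about 54-57% |
| 90 | 80%/88% | about 93-95% |
| 90 | 90%/92% | about 93-94% |
| 30 | 3%/10% | about 18-24% |

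Good adherence does not remove the error: with 80% of visits exactly on Day 113, a true 60% still reads about 76%. At 80%/88% the curve reached 100% in about 19-29% of trials although not everyone had responded. With every visit on Day 113 the error is zero.

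**Median.** At 70%/80%, 75%/85% and 90%/95% (n = 90) the median fell before Day 109 in every run and did not change. At 30%/40% (n = 90) a median was reported although fewer than half had responded in about 46-63% of trials. At placebo-like rates (n = 30, 3-10% at Week 16) a spurious median appeared in 2-8% of trials.

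**After placing Week 16 results on one scheduled day.** Without dropout, the end of the curve equals the observed proportion of first responders.

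**The case against.** The strongest reply is that the consequence is limited. The endpoint is tertiary and lies outside the fixed sequence H1 to H4. The by-visit responder rates for PASI75/90/100 are produced separately and are untouched. If few first responses fall at Week 16, the error is small: a true 92% reads 93-94%. All of this stands, and because the documents give no rates, the size for each PASI threshold cannot be known in advance.

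A reader might infer more than the documents support, in four ways.

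- **That the median is wrong in both arms.** It is not affected if half of the arm has responded before the Week 16 visits.
- **That the error vanishes only if all visits fall on one day.** It is also zero if no first response occurs at Week 16, or if everyone has responded.
- **That the curve ought to match the Week 16 responder rate.** Kaplan-Meier counts anyone who ever responded, including at unscheduled visits. The responder rate is status at Week 16 under nonresponder imputation. Someone who responds at Week 8 and then loses response counts in the first and not in the second, so the two can differ even after the fix.
- **That the log-rank test is invalid.** None of the work shows this. One simulation with equal arms (90 versus 30, 30%/40%, evenly spread visits) gave a type I error of 0.051 with actual dates and 0.051 with scheduled days.

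One further limit: a participant without a PASI at Week 16 is censored earlier under the SAP, so the mechanism concerns only those assessed at that visit.

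**Conclusion.** The point holds for the end of the Kaplan-Meier curve. Following SAP 4.4.3 as written overstates cumulative first response at Week 16 in any arm where visit dates vary and some first responses, but not all of those outstanding, occur at that visit. The excess is about 16 to 20 points at an assumed 45%/60%, 14 to 17 at 30%/40%, 5 to 7 at 80%/88% and 1 to 2 at 90%/92%. These sizes rest on assumed rates, no dropout and visit timing unrelated to response. The direction follows from the plan's own rules.

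The median and its interval are affected only if fewer than about half of an arm has responded before the Week 16 visits. The co-primary and key secondary results are not touched, and no error in the log-rank test has been shown.

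**What to change.** Amend SAP 4.4.3 as follows.

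- Use the scheduled day (Day 8, 15, 29, 57, 85 or 113) for a response found at a scheduled visit.
- Censor nonresponders with a PASI at Week 16 on Day 113, with events preceding censorings at ties.
- Place a response found at an unscheduled visit inside a visit window on that window's scheduled day. Otherwise keep its actual day.
- Keep the last-observed-PASI rule for participants without a Week 16 PASI. Express that date on the same day scale, so that the same effect does not reappear at an earlier visit.
- Use these times for the curve, the median and the log-rank test alike.

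The cost is a short SAP change and a small programming change. Times are rounded by up to 4 days for in-window visits, and by more for a scheduled visit held out of window. That is finer than the 4-week gap between the later PASI readings.

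Keeping actual event dates and censoring Week 16 nonresponders on a common day after the window, such as Day 118, also repairs the arithmetic, but it is the weaker choice. It extends follow-up past the last PASI and normally past the Week 16 dose, at which placebo participants start bimekizumab and the Initial Treatment Period ends. If used at all, it should be labelled as a convention.

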4.5 Safety analyses

If not specified otherwise, all safety summaries and listings will be created for all study participants in the SS.

The MS will be used for summaries of safety that include data from the MTP and the AMS will be used for Initial and Maintenance Treatment Period (combined) summaries.

4.5.1 Extent of exposure

Summaries for exposure will be provided. This will consist of a descriptive summary of study medication duration in days. In addition, total study medication duration and time at risk will be summarized in participant-years by treatment group and treatment period (ie, the ITP, the MTP, the Initial and Maintenance Treatment Period (combined)). The cumulative study medication duration will be summarized for study participants exposed for given durations of time, the following categories for duration will be used:

- >0 weeks
- >=16 weeks
- >=24 weeks
- >=32 weeks

Definitions for study medication duration and time at risk in days are provided in this section. Time at risk will be summarized in participant-years. Time at risk in participant-years is calculated by dividing the time at risk in days by 365.25.

Throughout this section, date of last clinical contact for each study participant is defined as the maximum of [last study visit date including SFU visit (including unscheduled SFU), last AE start date (including imputed AE start dates), date of study termination or completion, last date of IMP administration].

4.5.1.1 Exposure during the ITP

Definitions for study medication duration (days) and time at risk (days) during the ITP are provided as follows:

Study medication duration (days)

Date of last dose in the ITP – date of first dose in the ITP + 28

The use of +28 reflects the dosing interval of Q4W.

- If the date of last dose in the ITP + 28 days extends to a date beyond the date of first dose of the MTP, then this calculation reverts to:

Date of first dose in the MTP – date of first dose in the ITP + 1

- For study participants who died during the ITP, if date of last dose in the ITP + 28 days extends beyond the date of death, then this calculation reverts to:

Date of death – date of first dose in the ITP + 1

- For study participants who discontinue the ITP early, if date of last dose in the ITP + 28 days extends beyond the date of the last visit (including PEOT, not including SFU), then this calculation reverts to:
 - *Date of last visit – date of first dose in the ITP + 1*

Time at risk (days)

For study participants who complete the final visit of the ITP (Week 16 visit) and continue to the MTP:

$$\text{Date of first dose in the MTP} - \text{date of first dose in the ITP} + 1$$

For study participants who died during the ITP:

$$\text{Date of death} - \text{date of first dose in the ITP} + 1$$

For study participants who discontinue the ITP early or who complete the ITP but not continue to the MTP, use the minimum of the following:

- *The total number of days in the ITP (112 days). For AEs that emerged after 112 days but still within the 119 days window, those AEs would be classified as TEAE, but will be excluded from the output based on the ITP. However, these AEs will be included in the AE summaries for Initial and Maintenance Treatment Period (combined).*
- *Date of last clinical contact – date of first dose in the ITP + 1*

